### 3. STUDY OBJECTIVES

The objective of this study is to validate the Philips DXL ECG Algorithm works as intended in the HeartStart Intrepid Monitor/Defibrillator after a software update was completed to address instances of high impedance. This study will also determine the diagnostic quality of the 12-lead ECG tracing from the HeartStart Intrepid Monitor/Defibrillator.

#### 3.1 Endpoints

##### 3.1.1 Primary Endpoints

Validation

- Number of failures of ‘unable to obtain a 12-lead ECG’ with the Philips HeartStart Intrepid Monitor/Defibrillator
- Number of diagnostic quality 12-lead ECG tracings from the Philips HeartStart Intrepid Monitor/Defibrillator

Safety

- Frequency and severity of unexpected adverse events
- Unanticipated adverse device effects (UADE)

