#### 3.2 Hypotheses

Hypothesis 1A: We hypothesize that a 12-lead ECG will be obtained greater than 90% of the time with a target goal of 99%.

$$H_{0A}: \pi_A \leq 0.90$$

$$H_{1A}: \pi_A > 0.90$$

Document ID:	CC_TC_ECR_Intrepid 12Lead_2022_11549	Document title: Philips HeartStart Intrepid 12-lead ECG Study – The ICE study Protocol	Classification:	For internal use
Modified:	12SEP2022		Clinical Protocol	Author:
Version:	2.0	Approver:		Ref to Page 2
Status:	Final	Page:		23 of 51

Hypothesis 1B: We hypothesize that 12-lead ECG tracings will be of diagnostic quality greater than 90% of the time with a target goal of 99%.

$$H_{0B}: \pi_B \leq 0.90$$

$$H_{1B}: \pi_B > 0.90$$

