The Philips HeartStart Intrepid Monitor /Defibrillator is currently released for sale in the European market. It will be submitted to the FDA for 510(k) clearance during the time of this study. In the United States it is considered a Class II medical device. For the purposes of this study, the device will only be able to be used for monitoring and no clinical decision will be made based on the results obtained. None of the defibrillator accessories will be available for use. The Philips HeartStart Intrepid Monitor /Defibrillator used for this study is considered an investigational medical device. The sponsor considers this study to be a minimal risk study with a non-significant risk device. As monitor/defibrillator is not implantable, not supporting or sustaining life, not curing, mitigating, or treating disease, or otherwise preventing impairment of human health, and does not otherwise presents a potential for serious risk to the health, safety, or welfare of a subject.

A 12-lead ECG will be acquired three times (3) for each participant. The 12-lead ECG does not continuously record. As the leads are connected to the electrodes, markers will be placed for the three-lead and five-lead configurations. The Philips HeartStart Intrepid Monitor /Defibrillator has a 12-lead ECG preview screen that will allow the site staff to determine if a 12-lead ECG can be acquired. Once the 'start acquire' button is pushed, the recording will start and approximately 10 to 12 seconds a 12-lead ECG will be recorded. If the 12-lead does not have a good signal, no recording will be able to be obtained.

Participants will be randomized to electrodes that are either from an unopened package or have had the package open for 24 hours or 30 days. The 30-day electrodes will have a window of being opened plus or minus 10 days. The length of time the package is open is proportional to the amount of conductive gel that has dried on the electrode. The longer the electrode package is open, the drier the conductive gel and the higher the impedance. The dried electrodes will be used to simulate high impedance.

Document ID:	CC_TC_ECR_Intrepid 12Lead_2022_11549	Document title: Philips HeartStart Intrepid 12-lead ECG Study – The ICE study Protocol	Classification:	For internal use
Modified:	12SEP2022	Clinical Protocol	Author:	[name]
Version:	2.0		Approver:	Ref to Page 2
Status:	Final		Page:	27 of 51

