ECG, the 12-lead ECG preview screen will be made available, the study staff will then place the remaining electrodes and determine if a 12-lead ECG can be obtained. If the 12-lead ECG cannot be obtained and the participant has been randomized to either the 1 day or 30 day electrodes, the electrodes will be swapped for electrodes from an unopened package. If the 12-lead ECG cannot be obtained after the electrodes have been changed, this will be considered a 'Fail.'

Source: Derek R. Cooney: Cooney's EMS Medicine: www.accessemergencymedicine.com Copyright © McGraw-Hill Education. All rights reserved.

After the ECG electrodes are placed, the patient will have their SpO2 and noninvasive blood pressure monitored as detailed in the instructions for use. The blood pressure cuff will be placed on the opposite arm from the SpO2 sensor.

Once all electrodes and monitoring functionality is placed, the patient will be given time to relax. Once relaxed, the participant will be asked to lay quietly for up to 15 minutes while the device collects the ECG and other vitals are monitored. See the table below for frequency. After the readings are completed, all equipment will be removed and the participant will be free to leave the laboratory.

Data Acquisition frequency.

Monitoring Functionality	Data Acquisition by device
Non-Invasive Blood Pressure	Minute 0, Minute 5, and Minute 10
12-Lead ECG	Immediately after the NBP cuff deflates (approximately minute 1, minute 6 and minute 11)
SpO 2	Continuously (1 minute intervals)

It is anticipated for the first 1 to 3 participants, that a Philips Engineer and members of the Philips Clinical Team will be on-site to observe the study. The Philips Engineer will be able to troubleshoot any of the issues experienced with the capture of the 12-lead ECG on the HeartStart Intrepid.

Document ID:	CC_TC_ECR_Intrepid 12Lead_2022_11549	Document title: Philips HeartStart Intrepid 12-lead ECG Study – The ICE study Protocol	Classification:	For internal use
Modified:	12SEP2022		Author:	[name]
Version:	2.0	Clinical Protocol	Approver:	Ref to Page 2
Status:	Final		Page:	34 of 51

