### 7.4 Data Processing and Scoring

Electrocardiograms from all ECG monitoring events are to be presented to the independent reviewer. Participant Number, age and gender are pre-printed on the ECG. The reviewer will make an assessment of each ECG and document the results in the case report form.

ECGs will be examined in each of the following criteria. We have assumed that the HeartStart Intrepid Monitor/Defibrillator runs at a paper speed of 25 mm/s, that is, each second is represented by five large squares.

- a. 1mV calibration, any lead, as the number of large squares
  - A number OR not readable.
- b. Heart rate, as displayed on the ECG
  - A whole number, as beats per minute, OR missing.
- c. Heart rate, as the number of large squares in an RR interval
  - A number OR not readable.
  - Enter one small square as 0.2 large square.
  - Enter a minimum and a maximum if the rhythm is irregular.
- d. Cardiac axis: not readable OR normal OR abnormal.
- e. Rhythm: not readable OR normal OR abnormal.
- f. P wave, any lead: not readable OR normal OR abnormal.
- g. PR interval, any lead: not readable OR normal OR abnormal.
- h. QRS complex, any lead: not readable OR normal OR abnormal.
- i. ST segment, any lead: not readable OR normal OR abnormal.
- j. T wave, any lead: not readable OR normal OR abnormal.
- k. QT interval, any lead: not readable OR normal OR abnormal.
- l. U wave, any lead: not readable OR normal OR abnormal.

Document ID:	CC_TC_ECR_Intrepid 12Lead_2022_11549	Document title: Philips HeartStart Intrepid 12-lead ECG Study – The ICE study Protocol	Classification:	For internal use
Modified:	12SEP2022		Author:	[name]
Version:	2.0		Approver:	Ref to Page 2
Status:	Final		Page:	35 of 51
			Clinical Protocol	

- m. Overall impression ONE OF not interpretable OR normal OR abnormal, but no action required OR abnormal and requires immediate action.

An ECG from the printed patient record is considered to be of diagnostic quality when every part of the waveform in every lead is readable.

SpO2 data and NBP data will be utilized to troubleshoot any 12-lead ECG tracings that are not readable or abnormal.

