## 10. STATISTICAL CONSIDERATIONS

The statistical analysis plan has been incorporated into this protocol. It is not a stand-alone document.

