### 10.1 Sample Size Determination

Each hypothesized endpoint estimates a target proportion of 99% with an expectation to be statistically better than 90%. Using a one-sided exact test, with 80% power and alpha of 0.025, a sample size of 56 evaluable subjects is required.

Both hypothesized endpoints must be met for study success, therefore alpha level adjustments are not necessary to address familywise error.

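### Endpoint 1B is worded and scored per tracing, three per participant, but sized on 56 subjects; the plan states neither the 1B denominator nor how three tracings become one result

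*Combined protocol and SAP*

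**What the plan says.** Section 3.1.1 lists 1B as "Number of diagnostic quality 12-lead ECG tracings from the Philips HeartStart Intrepid Monitor/Defibrillator". Section 3.2 puts the hypothesis on the same footing: "We hypothesize that 12-lead ECG tracings will be of diagnostic quality greater than 90% of the time", with a null of 90% and a target of 99%.

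Section 6.1 plans repeats: "A 12-lead ECG will be acquired three times (3) for each participant". The table in section 7.2 times them: "Immediately after the NBP cuff deflates (approximately minute 1, minute 6 and minute 11"). In section 7.4 the unit of scoring is again the single ECG: "The reviewer will make an assessment of each ECG and document the results in the case report form". The definition there begins "An ECG from the printed patient record is considered to be of diagnostic quality" and goes on to require that all of the waveform be readable in all leads. It contains no participant-level rule.

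The sizing uses another unit. For each hypothesized endpoint, section 10.1 takes 90% against 99%, a one-sided exact test, alpha 0.025 and 80% power, and concludes that "a sample size of 56 evaluable subjects is required". Section 10.4.2 says only that each primary endpoint gets a one-sided exact binomial test and that both must succeed. Section 10.4.5 plans no sensitivity analysis. Section 10 notes that "The statistical analysis plan has been incorporated into this protocol", so there is no separate SAP in which the rule could stand.

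**The concern.** An exact binomial test needs independent trials and a defined number of them. For 1B the denominator could be 56 participants or up to 168 tracings. Three tracings from one person within about ten minutes, with no electrode change scheduled between them, are unlikely to be independent.

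If tracings are pooled, as the endpoint wording invites, the 2.5% level is not assured. If the participant is the unit, the plan still has to say which result counts for a person with three. Because both co-primary endpoints must succeed, a choice made after the readings are known could decide the study.

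**Working it through.** **Inputs.** Null 0.90 and target 0.99 (section 3.2). One-sided alpha 0.025, power 80%, 56 evaluable subjects (section 10.1). Three ECGs per participant (section 6.1), so at most 56 × 3 = 168. The correlation between tracings of one participant is not in the documents. It is assumed over the range 0 to 1, equal among the three tracings (beta-binomial model).

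**1. The plan's own figure.** The normal approximation is n = [(1.960·√(0.9·0.1) + 0.842·√(0.99·0.01)) / 0.09]² = 55.7, hence 56. By exact search, the smallest n that meets both targets is 54 (pass at 53; alpha 0.0237, power 0.898). At 56 the pass mark is 55:
- alpha = 0.9⁵⁶ + 56·0.9⁵⁵·0.1 = 0.0027 + 0.0170 = 0.0198
- power = 0.99⁵⁶ + 56·0.99⁵⁵·0.01 = 0.5696 + 0.3222 = 0.892

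The figure of 56 is therefore sound for one result per subject.

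**2. All tracings in the exact test.** With n = 168 the pass mark is 159 (nominal alpha 0.0233). The true rejection probability at a 90% rate comes from convolving 56 beta-binomial clusters of three:

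| Assumed correlation | Type I error |
|---|---|
| 0 | 2.3% |
| 0.05 | 2.9% |
| 0.1 | 3.4% |
| 0.3 | 5.9% |
| 0.5 | 8.3% |
| 1 | 17.6% |

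It passes 2.5% at a correlation of about 0.016. That threshold is low partly because the nominal level is already 2.33%.

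**3. Combining rules when 90% and 99% are per-tracing rates.** Let q be the probability that a participant succeeds under the rule. The pass probability is then P(Bin(56, q) ≥ 55).

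| Assumed correlation | Any of three, tracing rate 90% | Two of three, tracing rate 90% | All three, tracing rate 99% |
|---|---|---|---|
| 0 | 99.9% | 53% | 50% |
| 0.3 | 71% | 7.8% | 65% |
| 0.5 | 36% | 3.7% | 73% |

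For example, any-of-three at correlation 0.3 has q = 0.9809 and passes 71% of the time. All-three at correlation 0 has q = 0.99³ = 0.9703, giving 50% power; it reaches 80% only at a correlation of about 0.70.

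**4. One total, different outcomes.** Take 159 of 168 diagnostic. Pooled, it passes (p = 0.023).
- If three participants fail all their tracings, the participant count is 53/56 under any of the three rules, which fails (p = 0.176).
- If nine participants fail one tracing each, any-of-three or two-of-three gives 56/56 and passes (p = 0.003), while all-three gives 47/56 and fails (p = 0.95).

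**5. Denominator.** Suppose that of 56 participants one has no tracing and one has a non-diagnostic tracing. Excluding the first gives 54/55, which passes (p = 0.022). Counting that participant as a failure gives 54/56, which fails (p = 0.072).

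**The case against.** The best reply is that the documents already point to the participant. Section 10.1 sizes each hypothesized endpoint, 1B included, on subjects. Section 10.4.1 speaks of evaluable participants, and section 11.5.2 of a primary endpoint for a given participant. Nowhere does the plan say that tracings will be pooled, and doing so would depart from the only stated sample size. This stands as far as it goes, and the pooled error rates describe a reading that the wording permits, not an announced analysis. But section 10.1 fixes the size and not the test, and a participant-level unit still needs a rule for three tracings.

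The objection to the combining-rule figures also stands. A reader might take the 71% for any-of-three as the type I error of a participant-level test. It is not. If the 90% null is defined for the participant result under whichever rule is chosen, the exact test holds at 1.98% for any rule and any correlation. The figures show that a combining rule tests a different quantity from a per-tracing rate. The all-three power loss likewise arises only if 99% is a per-tracing rate. The plan proposes none of these rules.

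A reader might also see a further change of unit in section 10.5, which mentions the first three ECGs. Section 10.6 restates that pause rule by the first three participants, and a pause rule outside the hypothesis test has no bearing on alpha or power.

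**Conclusion.** The gap is real and should be closed before any 1B result is seen: a co-primary test has no stated denominator and no rule for three tracings. Followed literally on tracings, the test exceeds its 2.5% level at all but very small correlations. The excess is modest at 0.1 (3.4%) and large at 0.5 (8.3%). These sizes rest on assumed correlations, equal clusters of three and a beta-binomial model; only the direction is firm.

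One might infer that 56 is too few. The documents do not support that: with one result per participant and the rates defined for that result, alpha is 1.98% and power 89.2%.

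**What to change.** In sections 3.1.1, 3.2 and 10.4.2, state that the participant is the unit of the 1B exact test, with one pre-specified result each and with 0.90 and 0.99 defined for that result. Two rules would serve:
- **One tracing fixed by schedule**, for example the first scheduled acquisition, never replaced by a later one. This keeps the per-tracing meaning of the rates and the alpha and power of step 1 at any correlation. One failure is allowed at any number tested from 54 to 60.
- **All three tracings diagnostic**, with 90% and 99% restated as participant-level rates.

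State the denominator, including how a participant with no tracing counts.

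Report all tracings as supportive, with an interval that allows for clustering and for unequal numbers per person, since section 6.1 says that a poor signal gives no recording. One option is a Clopper-Pearson interval on an effective sample size of (Σm)² / Σm², where m is each participant's number of tracings. With three each this is 168² / (56 × 9) = 56. With 50 participants giving three and 6 giving one (an assumed example) it is 156² / 456 = 53.4. If all 168 pass, the lower limit at 56 is 0.025^(1/56) = 93.6%, against 97.8% if clustering is ignored.

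The cost is a protocol amendment in wording only; data collection and sample size do not change. Under the single-tracing rule the other tracings do not enter the primary 1B test, so a participant whose later tracings are unreadable can still count as a success.

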#### 3.2 Hypotheses

Hypothesis 1A: We hypothesize that a 12-lead ECG will be obtained greater than 90% of the time with a target goal of 99%.

$$H_{0A}: \pi_A \leq 0.90$$

$$H_{1A}: \pi_A > 0.90$$

Document ID:	CC_TC_ECR_Intrepid 12Lead_2022_11549	Document title: Philips HeartStart Intrepid 12-lead ECG Study – The ICE study Protocol	Classification:	For internal use
Modified:	12SEP2022		Clinical Protocol	Author:
Version:	2.0	Approver:		Ref to Page 2
Status:	Final	Page:		23 of 51

Hypothesis 1B: We hypothesize that 12-lead ECG tracings will be of diagnostic quality greater than 90% of the time with a target goal of 99%.

$$H_{0B}: \pi_B \leq 0.90$$

$$H_{1B}: \pi_B > 0.90$$

## 4. BOTH HYPOTHESES MUST BE MET FOR OVERALL STUDY SUCCESS. STUDY DESIGN

### 4.1 Overall Design

This is a clinical study performed in a single center for validation purposes, with all data collection occurring within a single visit.

Up to 60 (sixty) participants will be enrolled, for 56 (fifty-six) to complete data collection.

### 4.2 Rationale for Study Design

This clinical study is designed primarily as an engineering evaluation to validate the software functionality for the HeartStart Intrepid Monitor/Defibrillator. This study is necessary to confirm the device is functioning as designed prior to release of the software.

### 4.3 Sample size

Up to 60 (sixty) participants will be enrolled, for 56 (fifty-six) participants to complete data collection.

### 4.4 Study Duration and End of Study Definition

The total enrollment duration for an individual participant will not exceed one day; it is estimated that the entire study duration will not exceed one month.

Document ID:	CC_TC_ECR_Intrepid 12Lead_2022_11549	Document title: Philips HeartStart Intrepid 12-lead ECG Study – The ICE study Protocol	Classification:	For internal use
Modified:	12SEP2022	Clinical Protocol	Author:	[name]
Version:	2.0		Approver:	Ref to Page 2
Status:	Final		Page:	24 of 51

## 5. STUDY PARTICIPANTS

### 5.1 Study Sample Considerations

The software change was created to help with high impedance experienced with some patients while obtaining a 12-lead ECG. This high impedance can be a result of skin conditions (wet skin) or electrodes that have been exposed to air for extended periods of time. Extended exposure to air will dry out the electrodes prematurely and reduce their adhesive and conductive properties. The study will utilize electrodes from an unopened package, a package open for 24 hours and package open for 30 days. This will be a stratification factor for randomization.

The inclusion/exclusion do not specify any clinical conditions for enrollment, as the study does not plan to diagnose or confirm any medical conditions.

### 5.2 Inclusion Criteria

Inclusion criteria are as follows:

- Able to read, write, speak, and understand English
- Aged 29 days to 89 years
- Willing and able to provide informed consent and complete study procedures
- Willing to have Philips representatives present during study procedures.

### 5.3 Exclusion Criteria

Exclusion criteria are as follows:

- Known allergy to medical adhesives, silicone, or latex (per self-report)
- Any limitation or medical condition, including but not limited to physical or cognitive disability, that would affect the participant’s ability to complete study activities (per investigator)
- At the time of enrollment, current enrollment in any other interventional research study
- An employee, or residing family member of an employee, of a company that designs, sells, or manufactures monitor/defibrillator technology or related products (including Philips)

Document ID:	CC_TC_ECR_Intrepid 12Lead_2022_11549	Document title: Philips HeartStart Intrepid 12-lead ECG Study – The ICE study Protocol	Classification:	For internal use
Modified:	12SEP2022	Clinical Protocol	Author:	[name]
Version:	2.0		Approver:	Ref to Page 2
Status:	Final		Page:	25 of 51

## 5.4 Definitions of Enrollment and Screen Failures

Potentially eligible participants will be consented, if willing (see Section 7.1.2), and all participants who sign the consent form will be considered enrolled. Formal assessment of eligibility according to the criteria listed in Sections 5.2 and 5.3 will take place following consent, and any participants found to be ineligible at this point will be considered screen failures. The following data will be reported for screen failures:

- Sociodemographic data (age, sex, and race/ethnicity);
- Adverse events during the enrollment period;
- Reason/s for ineligibility.

Any participant that discontinues/is withdrawn from the study following randomization will be categorized as an early termination (see Section 11) rather than a screen failure, even if the discontinuation/withdrawal occurred prior to the participant beginning the study intervention.

## 5.5 Strategies for Recruitment and Retention

The participants will be of both sexes, with a wide body mass index (BMI) range, to support generalizability of results. Due to the small sample size, no firm parameters for these measures have been determined a priori.

This study is not limited to adult patients. It is anticipated that at least 30% of the sample will be under the age of 16.

It is anticipated that racial/ethnic minorities will represent at least 30% of the sample.

All participants will be enrolled within the US. Recruitment will be the responsibility of the site and will take place through recruitment of their internal databases. As this study involves only one visit, it is not likely that participants will drop-out or be lost to follow-up before study completion. No specific strategies for retention are required.

# 6. STUDY PRODUCT

## 6.1 Description of Intervention

The HeartStart Intrepid Monitor/Defibrillator Model 867172 is a lightweight, portable Monitor/Defibrillator with a large display. It provides four clinical modes of operation: Monitor, Manual Defibrillation/Synchronized Cardioversion, AED and Pacing. The HeartStart Intrepid is powered by a rechargeable Lithium-Ion battery, AC Power or DC power with use of a special DC

Document ID:	CC_TC_ECR_Intrepid 12Lead_2022_11549	Document title: Philips HeartStart Intrepid 12-lead ECG Study – The ICE study Protocol	Classification:	For internal use
Modified:	12SEP2022	Clinical Protocol	Author:	[name]
Version:	2.0		Approver:	Ref to Page 2
Status:	Final		Page:	26 of 51

Power Module. Available battery power is determined by viewing the battery power indicators located on the front of the device, the icon on the display, or by checking the gauge on the battery itself. Additionally, AC Power may be applied as a secondary power source and for continual battery charging.

This study will only utilize some of the monitoring functionality within the device. The HeartStart Intrepid Monitor/Defibrillator uses the Philips DXL ECG Algorithm. The Philips DXL ECG Algorithm produces precise and consistent ECG measurements that are used to generate interpretive statements. The process begins with the simultaneous acquisition of the twelve conventional leads along with patient demographic information.

The HeartStart Intrepid Monitor/Defibrillator utilized in this study will have software version 1.00.46. This software has been modified from its released version to account for instances of high impedance.

During the 12-lead ECG acquisitions, patients will have their SpO2 and blood pressure monitored.

The Philips HeartStart Intrepid Monitor /Defibrillator is currently released for sale in the European market. It will be submitted to the FDA for 510(k) clearance during the time of this study. In the United States it is considered a Class II medical device. For the purposes of this study, the device will only be able to be used for monitoring and no clinical decision will be made based on the results obtained. None of the defibrillator accessories will be available for use. The Philips HeartStart Intrepid Monitor /Defibrillator used for this study is considered an investigational medical device. The sponsor considers this study to be a minimal risk study with a non-significant risk device. As monitor/defibrillator is not implantable, not supporting or sustaining life, not curing, mitigating, or treating disease, or otherwise preventing impairment of human health, and does not otherwise presents a potential for serious risk to the health, safety, or welfare of a subject.

A 12-lead ECG will be acquired three times (3) for each participant. The 12-lead ECG does not continuously record. As the leads are connected to the electrodes, markers will be placed for the three-lead and five-lead configurations. The Philips HeartStart Intrepid Monitor /Defibrillator has a 12-lead ECG preview screen that will allow the site staff to determine if a 12-lead ECG can be acquired. Once the 'start acquire' button is pushed, the recording will start and approximately 10 to 12 seconds a 12-lead ECG will be recorded. If the 12-lead does not have a good signal, no recording will be able to be obtained.

Participants will be randomized to electrodes that are either from an unopened package or have had the package open for 24 hours or 30 days. The 30-day electrodes will have a window of being opened plus or minus 10 days. The length of time the package is open is proportional to the amount of conductive gel that has dried on the electrode. The longer the electrode package is open, the drier the conductive gel and the higher the impedance. The dried electrodes will be used to simulate high impedance.

Document ID:	CC_TC_ECR_Intrepid 12Lead_2022_11549	Document title: Philips HeartStart Intrepid 12-lead ECG Study – The ICE study Protocol	Classification:	For internal use
Modified:	12SEP2022	Clinical Protocol	Author:	[name]
Version:	2.0		Approver:	Ref to Page 2
Status:	Final		Page:	27 of 51

